4.4. Withdrawal Criteria

A subject may voluntarily discontinue participation in this study at any time or may be withdrawn at the discretion of the investigator. Record the primary reason for withdrawal in the electronic case report form (eCRF).

Subjects in the treatment holiday and control groups will be withdrawn from the study for:

- Pregnancy: positive urine pregnancy test.
- Clinically significant, potentially life-threatening (Grade 4) AE that in the clinical judgement of the investigator is possibly, probably or definitely related to belimumab.
- Liver chemistry abnormalities. Refer to details regarding liver chemistry abnormalities and withdrawal as specified in Section 6.4.1.

- Laboratory parameters: Demonstrate clinically important changes in laboratory parameters.
- Prohibited concurrent medication or therapy.

These subjects will complete the Week 52 Exit visit (except for dosing with belimumab) at the time of discontinuation and the16-week follow-up visit assessments at least 16 weeks after the withdrawal visit or last dose of belimumab as appropriate (see Section 6). The 6 month follow-up visit is scheduled only for those subjects in the treatment holiday or control groups.

Subjects in the long-term discontinuation group will be withdrawn from the study for:

- Pregnancy: positive urine pregnancy test.
- Laboratory parameters: Demonstrate clinically important changes in laboratory parameters.
- Have developed clinical evidence of significant, unstable or uncontrolled, acute or chronic diseases not due to SLE (i.e., cardiovascular, pulmonary, hematologic, gastrointestinal, hepatic, renal, neurological, malignancy or infectious diseases), or experienced an adverse event (AE) that could, in the opinion of the principal investigator, put the subject at undue risk.
- Have developed any other medical diseases (e.g., cardiopulmonary), laboratory abnormalities, or conditions (e.g., poor venous access) that, in the opinion of the principal investigator, makes the subject unsuitable for the study.

These subjects will complete the Week 52 visit assessments (see Section 6).

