5. STUDY TREATMENTS

5.1. Investigational Product and Other Study Treatment

Belimumab for intravenous (IV) infusion will be supplied in glass vials by GSK. The contents of the label will be in accordance with all applicable regulatory requirements. Detailed instructions on the preparation, administration and storage of belimumab are provided in the Pharmacy Manual. Belimumab IV solution should be prepared by a pharmacist. Reconstitute the 400 mg single use vial of belimumab with 4.8 mL sterile water for injection to yield a final concentration of belimumab 80 mg/mL. Remove an amount of normal saline from the infusion bag equivalent to the amount of belimumab to be added, add the reconstituted belimumab, and gently invert the infusion bag to mix the solution. After reconstitution and dilution in normal saline, the material is stable for up to 8 hours at 2-8°C or at room temperature. The characteristics of belimumab are summarized in Table 1.

Property	Belimumab
Formulation	Belimumab 400 mg per vial plus excipients (citric
	acid/sodium citrate/sucrose/polysorbate)
Dosage Form	Reconstituted solution
Unit dose strength	400 mg per vial (to contain 80 mg/mL when reconstituted
	with 4.8mL sterile water for injection [SWFI])
Physical description	White uniform lyophilised cake in a 20 mL vial
Manufacturer	Human Genome Sciences, Inc.
Route of administration	Intravenous

Table 1 Belimumab Characteristics

Subjects enrolled in the treatment holiday group will receive treatment with belimumab 10 mg/kg from Week 24 onwards **after** the initial 24-week treatment holiday period of the study has elapsed (see Section 3.1). At the start of the belimumab reintroduction period, subjects in the treatment holiday group will receive belimumab 10 mg/kg IV infused for over 1 hour every 28 days.

Subjects in the control group will receive belimumab 10 mg/kg IV infused for over 1 hour every 28 days from Day 0 onwards. Subjects in this group must be able to receive their first dose of belimumab on Day 0 of this study 4 weeks (minimum of 2 weeks, maximum of 8 weeks) after the last dose in the BEL114333 open-label continuation study.

Subjects in the long-term discontinuation group will not receive belimumab at any point in this study.

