- 15. Biological Markers include FACS of peripheral lymphocytes: B lymphocytes (CD20+, CD20+/27+ memory, CD20+/27- naïve, CD20+/69+ activated, CD20+/138+ plasmacytoid, CD19+/27^{BRIGHT}/38^{BRIGHT} SLE subset and CD20-/138+ plasma cells). Note: B cell markers will not be collected at the 6-month follow up visit for subjects in the long-term discontinuation group as this visit does not apply to this subject group.
- 16. Only subjects in the control group will receive belimumab 10 mg/kg during Weeks 0 through 20 inclusive; subjects in the control group must be able to receive the first dose of belimumab in this study 4 weeks (minimum of 2 weeks, maximum of 8 weeks) after the last dose in their previous open-label continuation study Subjects in the control group and treatment holiday groups will receive belimumab from Weeks 24 through 48 although subjects in the treatment holiday group may be treated with belimumab prior to Week 24 as determined by the investigator in the event of increased SLE activity. When belimumab therapy is re-started, subjects in the treatment holiday group will remain under clinical supervision for 3 hours after completion of the first 2 infusions. At the Week 52 visit, only subjects in the treatment holiday and control groups who are continuing belimumab therapy beyond this time will be dosed.

2012N154810_06

CONFIDENTIAL

2018N381035_00 BEL116027

Table 3 Time and Events Table (Additional Years)

Study Visit (Weeks) ¹	4	8	12	16	20	24	28	32	36	40	44	48
Study Day	28 ±7d	56 ±7d	84 ±7d	112 ±7d	140 ±7d	168 ±7d	196 ±7d	224 ±7d	252 ±7d	280 ±7d	308 ±7d	336 ±7d
Efficacy Assessments												
Disease Activity Scales: SELENA SLEDAI, SLE Flare Index, and PGA ²						х						Х
SLICC/ACR Damage Index												Х
Safety Assessments												
Symptom-driven Physical Exam						Х						Х
Record Concurrent Medications	Х	Х	Х	Х	Х	Х	Х	Х	Х	Х	Х	Х
Adverse Events	Х	Х	Х	Х	Х	Х	Х	Х	Х	Х	Х	Х
Vital Signs ^{3, 4}	Х	Х	Х	Х	Х	X	Х	Х	Х	Х	Х	Х
Laboratory Assessments												
Haematology & Modified Chem 20 (non- fasting) ^{3, 5}						Х						Х
Urinalysis ^{5, 6}						Х						Х
Spot urine (protein to creatinine ratio) ^{3, 5, 6}						Х						Х
Urine Pregnancy Test ^{3, 5, 7}	Х	Х	Х	Х	Х	Х	Х	Х	Х	Х	Х	Х
C3, C4, Anti-dsDNA Autoantibodies ^{3, 5}						Х						Х
IgG ^{3, 5, 8}												Х
IgA & IgM ^{3, 5, 8}												Х
Exploratory Lab Assessments												
Immunogenicity ^{3,9}						Х						Х
B cell Markers ¹⁰												Х
Investigational Product												

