8.1.4. Safety Analysis

AEs will be graded for severity by the investigator using Adverse Event Severity Grading Tables (Appendix 6) or the grades in Section 6.4.8, as appropriate. The frequency of AEs will be tabulated by MedDRA system organ class and preferred term and by treatment groups, according to the treatment group that the subjects were assigned to in the BEL116027 study. Additional analysis may be performed based on event rates adjusting for subject-years on study agent. The number of subjects with AEs and the incidence rate of AEs will be summarised in each 6-month time interval. AEs will also be summarised by MedDRA SOCs and preferred terms for those that are considered to be at least possibly related to study agent and those that are considered to be severe (Grade 3 and Grade 4). Discontinuations due to AEs will be summarised.

The frequency of laboratory abnormalities will be tabulated by treatment group. Laboratory values will be assessed for significant changes from baseline. Laboratory toxicity will be graded using Adverse Event Severity Grading Tables when possible. Shift tables will be used to determine if subjects move from normal to abnormal during the course of the study. Shifts of ≥ 2 grades and Grade 3 or Grade 4 laboratory abnormalities will be summarised.

Immunogenicity (anti-belimumab antibodies) will be summarized at baseline and during treatment and follow-up.

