8. SAFETY ANALYSES

The safety analyses will be based on the ITT population, unless otherwise specified.

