8.1. Adverse Events Analyses

Adverse events analyses including the analysis of adverse events (AEs), serious adverse events (SAEs), and other significant AEs will be based on GSK Core Data Standards. The details of the planned displays are provided in Appendix 11: List of Data Displays.

Adverse events will be coded to the current MedDRA dictionary version available at the time of reporting.

Only treatment emergent AEs will be summarized (see Section 13.4.1). Any AEs that were ongoing in the upon entry into this will be listed and flagged with a footnote

An overall summary of AEs will be presented showing the number (%) of subjects with at least one of the following: AE, related AE, SAE, severe AE, SAE and/or severe AE, AE resulting in study treatment discontinuation, and deaths.

The number of events and the number (%) of subjects experiencing an AE by SOC, SOC and PT, and PT will be summarized for each of the AE categories below.

- All
- Serious
- Severe
- Study agent Related
- Resulting in discontinuation of study treatment

The data will be sorted by overall decreasing frequency of the SOC, by overall decreasing frequency of the SOC and then decreasing frequency of PT within the SOC, and by overall decreasing frequency of the PT, as applicable. Only SOCs with observed AE PTs will be presented. If the frequency for any two or more adverse events is equal, the events will be presented in alphabetical order by SOC/PT as applicable.

Summaries of AEs frequency by SOC and severity will also be provided. For these displays, the number and percentage of subjects will be summarized as mild, moderate, or severe based on the maximum severity observed across all PTs within the SOC for a given subject.

The hierarchical relationship between MedDRA SOCs, PTs, and verbatim text will be displayed in a table for all AEs.

A listing of which subjects reported each AE will be produced. AEs will be grouped and sorted by SOC and PT. A listing of Infusion Related Systemic Reactions will be produced.

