13.4. Appendix 4: Study Phases and Treatment Emergent Adverse Events

13.4.1. Treatment Phases

- Visits, assessments and events will be classified according to the time of occurrence relative to the following cut-point dates for each treatment group.
- For convenience and ease of data presentation, the 52-Week Treatment Phase has the same name designation for all three treatment groups, even though the LTC group does not receive treatment at all during this phase and the TH group receives treatment for only the second half of the phase.
- Only the TC and TH groups are eligible to participate in the Maintenance Phase.
- If an AE start date falls on the Day 0 date, then it will be considered treatment emergent (i.e., fall in the 52-week treatment phase). If a concomitant medication start date falls on the Day 0 visit date, the concomitant medication will be considered to fall in the 52-week treatment phase. Any other assessments that fall on the Day 0 visit date will be considered to occur in the pre-study phase.
- For the TC group, if the first infusion date differs from the Day 0 visit date, then the first infusion date will be used as the phase cut-point.
- Other than Day 0, if an assessment or event occurs on the same date as a phase cutpoint, then the event will be considered to fall in the previous phase. For example, if a new prednisone dose starts on the same date as the Week 24 visit date and then continues for a total of 7 days, then the first day of that prednisone dose will fall into the Holiday Phase and the remaining 6 will fall into the Re-start phase.
- For AEs, if the AE Onset date is missing, then the AE will be considered to occur in the 52-week treatment phase.
- For the TH group, a subject who re-starts treatment prior to Week 24 will not have a Re-Start phase.

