13.11.7. Safety Tables

Safety:	Safety: Tables					
No.	Population	Title	Programming Notes	Priority Headline Results Denoted by H		
Concor	mitant Medicati	ons				
3.1.	ITT	Concomitant Medications by ATC Level 1 and ATC Level 4 Term for the 52-Week Treatment Phase	ICH E3			
Study A	Agent Exposure	9				
3.2.	ITT	Study Agent Exposure (52-Week Treatment Phase)	ICH E3			
SLICC						
3.3.	ITT	SLICC/ACR Damage Index Change from Baseline (52- Week Treatment Phase)	Other/exploratory endpoint			
Advers	e Events		·			
3.4.	ITT	Adverse Events (52-Week Treatment Phase)	Benlysta standard	Н		
3.5.	ITT	Adverse Events by SOC (52-Week Treatment Phase)	Benlysta standard			
3.6.	ITT	Serious Adverse Events by SOC (52-Week Treatment Phase)	Benlysta standard			
3.7.	ITT	Study Agent Related Adverse Events by SOC (52-Week Treatment Phase)	Benlysta standard			
3.8.	ITT	Adverse Events Resulting in Study Agent Discontinuation by SOC (52-Week Treatment Phase)	Benlysta standard			

Safety:	Safety: Tables				
No.	Population	Title	Programming Notes	Priority Headline Results Denoted by H	
3.9.	ITT	Adverse Events by SOC and PT (52-Week Treatment Phase)	ICH E3	Н	
3.10.	ITT	Serious Adverse Events by SOC and PT (52-Week Treatment Phase)	Benlysta Standard	Н	
3.11.	ITT	Study Agent Related Adverse Events by SOC and PT (52-Week Treatment Phase)	ICH E3		
3.12.	ITT	Adverse Events Resulting in Study Agent Discontinuation by SOC and PT (52-Week Treatment Phase)	IDSL	Н	
3.13.	ITT	Adverse Events by PT (52-Week Treatment Phase)	Benlysta Standard		
3.14.	ITT	Serious Adverse Events by PT (52-Week Treatment Phase)	Benlysta Standard		
3.15.	ITT	Study Agent Related Adverse Events by PT (52-Week Treatment Phase)	Benlysta Standard		
3.16.	ITT	Adverse Events Resulting in Study Agent Discontinuation by PT (52-Week Treatment Phase)	Benlysta Standard		
3.17.	ІТТ	Common (>5%) Non-Serious Adverse Events by SOC and PT (52-Week Treatment Phase) (Number of Subjects and Occurrences)	FDAAA, EudraCT		
3.18.	ІТТ	Serious Adverse Events by SOC and PT (52-Week Treatment Phase) (Number of Participants and Occurrences)	FDAAA, EudraCT	Н	
3.19.	ITT	Adverse Events by SOC and PT and Maximum Severity (52- Week Treatment Phase)	IDSL		

Safety:	afety: Tables					
No.	Population	Title	Programming Notes	Priority Headline Results Denoted by H		
3.20.	ITT	Relationship Between System Organ Class and Verbatim Text (52-Week Treatment Phase)	IDSL			

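### The AE-discontinuation category counts only stopping of study treatment, so no AE table shows which adverse events led untreated long-term discontinuation subjects to leave the study

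*SAP*

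**What the plan says.** SAP 8 sets the population: "The safety analyses will be based on the ITT population, unless otherwise specified". SAP 4 defines ITT as everyone enrolled apart from screen failures, so LTD is included.

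The overall summary in SAP 8.1 covers "AE, related AE, SAE, severe AE, SAE and/or severe AE, AE resulting in study treatment discontinuation, and deaths". In SAP 13.11.7, Tables 3.8, 3.12 and 3.16 carry the discontinuation category under the term study agent. Table 3.12, for example, is titled "Adverse Events Resulting in Study Agent Discontinuation by SOC and PT (52-Week Treatment Phase". Tables 3.4 and 3.12 are in the headline package. Listing 20 uses the term study treatment.

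On exposure, Protocol 5.1 states: "Subjects in the long-term discontinuation group will not receive belimumab at any point in this study". SAP 13.4.1 applies the 52-week treatment phase label to all groups, "even though the LTC group does not receive treatment at all during this phase" (LTC there evidently means LTD). For the first part of the study the Year 1 Time and Events Table says: "Only subjects in the control group will receive belimumab 10 mg/kg during Weeks 0 through 20 inclusive". The treatment holiday (TH) group restarts at Week 24.

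On withdrawal, Protocol 4.4 withdraws LTD subjects who have "experienced an adverse event (AE) that could, in the opinion of the principal investigator, put the subject at undue risk". Protocol 8.1.4 says: "Discontinuations due to AEs will be summarised". It does not limit that summary to dosed subjects, and the narrower SAP wording is not among the changes listed in SAP 2.1.

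**The concern.** The category needs a study treatment to stop. LTD subjects have none, so an adverse event that ends their participation does not meet the definition. The same kind of event in a treatment control (TC) subject, leading to the end of dosing, does meet it. The liver rules in Protocol 6.4.1 illustrate this. A dosed subject who meets a stopping criterion has belimumab discontinued, whereas an LTD subject who meets the same criterion is handled under the Section 4.4 withdrawal criteria. If both are recorded as AEs, only the first fits the category.

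The study exists to describe what happens when belimumab is stopped. The results are descriptive, so side-by-side tables carry the safety message. A 0 printed for LTD in a headline table would read as an observation when it follows from the definition. The SAP did adapt other rules to the off-drug groups: treatment emergence for TH and LTD runs from Day 0 with no dose required, and exposure is not calculated for LTD. The discontinuation category was not adapted.

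**Working it through.** **Inputs.** Enrolled numbers (SAP 2.3): LTD 39, TC 29, TH 12; total 39 + 29 + 12 = 80, as stated there. Prescribed infusions (SAP 13.6.2): TC 13, TH 7. The risk p of an AE leading to withdrawal over 52 weeks is not in the documents. I assume 5%, with a range of 3% to 10%, equal across groups and at constant hazard.

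**Step 1: reproduce the plan's infusion counts.** Four-weekly dosing at Weeks 0 to 48 gives 48/4 + 1 = 13 (TC). Weeks 24 to 48 give (48 − 24)/4 + 1 = 7 (TH). Both agree with the SAP. LTD has 0.

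**Step 2: apply the category as worded to each group.**

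| Group | Enrolled | Study infusions | Can the category be met? |
|---|---|---|---|
| TC | 29 | 13 | Yes, throughout 52 weeks |
| TH | 12 | 7 | Yes after re-start (28 of 52 weeks); holiday withdrawals not addressed |
| LTD | 39 (39/80 = 48.75%) | 0 | No treatment to discontinue |

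**Step 3: look for another AE display that would catch an LTD withdrawal.** SAP 13.11.7 has no table of AEs leading to study withdrawal. SAP 5.1 note 1 says that some tables show only TC and TH, without naming them. If LTD is shown, the cell is zero or undefined. If LTD is omitted, the group has no AE-discontinuation result at all. On either reading, LTD withdrawals caused by AEs are missing from these tables.

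**Step 4: illustrative size.** The expected LTD count is 39p, and the chance of at least one is 1 − (1 − p)^39. For TH, the expected count over 52 weeks is 12p; within the 28 on-drug weeks it is 12[1 − (1 − p)^(28/52)].

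| p (assumed) | LTD expected | Chance of ≥1 in LTD | TC expected (29p) | TH, 52 weeks | TH, on-drug weeks |
|---|---|---|---|---|---|
| 3% | 1.17 | 69.5% | 0.87 | 0.36 | 0.20 |
| 5% | 1.95 | 86.5% | 1.45 | 0.60 | 0.33 |
| 10% | 3.90 | 98.4% | 2.90 | 1.20 | 0.66 |

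Under the category as worded, the LTD column contributes nothing at any p.

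**The case against.** The derivation of the flag cannot be seen. SAP 8.1 defers to the sponsor's data standards, and neither the eCRF nor the mock shells are in the documents. The SAP also uses treatment loosely for LTD: it gives the group a treatment phase, treatment-emergent AEs and a drug-related category. A site might therefore tick the discontinuation field for an LTD subject. This stands as a limit on certainty, and it is why the LTD cell is described as a structural zero or undefined. It does not supply a rule.

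Withdrawals are also visible elsewhere. Tables 1.5, 1.7 and 1.8 and Listing 5 deal with disposition, time to withdrawal and reasons; Figure 1.1 (time to withdrawal) is a headline display; Listing 13 gives all AEs. This stands in part: the fact of withdrawal, and perhaps its reason, will be reported. None of these outputs is specified to link the reason to the adverse event.

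Protocol 8.1.4 does not promise a breakdown of study withdrawals by SOC and PT, and no document shows that the recorded withdrawal reason is tied to a particular AE. Both points are correct, and the fix allows for them.

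**Conclusion.** The concern holds for LTD. As worded, the AE-discontinuation category does not apply to 39 of 80 enrolled subjects, and their AE-driven withdrawals appear as such in no AE table, although Protocol 4.4 allows for them and Protocol 8.1.4 promises a summary. The size rests entirely on the assumed risk: about 2.0 uncounted LTD withdrawals at 5% (1.2 to 3.9 at 3% to 10%). The mismatch in definition does not depend on that assumption.

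The documents do not support four stronger readings that a reader might infer:

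- *TH is also zero by construction.* It is not. TH subjects restart at Week 24 and are prescribed 7 infusions. An AE that starts in the holiday and leads to stopping after re-start could count. The coding of an AE that prevents re-start is undefined. SAP 7 commits to separate holiday and re-start results for efficacy only. For TH the point is reduced opportunity and a missing rule.
- *The table makes stopping belimumab look safer whatever the truth.* The AE, SAE, severe AE and death rows need no drug exposure, and for LTD and TH they count from Day 0.
- *More than half of follow-up cannot register an event.* Planned off-drug time is 39 × 52 + 12 × 24 = 2316 of 4160 subject-weeks, but the row counts subjects, and 288 of those weeks are TH holiday time.
- *TC would probably exceed LTD by artefact.* At 5% that probability, 1 − 0.95^29 = 77%, is simply the chance of at least one TC event once LTD is fixed at zero.

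**What to change.** In SAP 8.1 and Table 3.4, add a category for AEs leading to withdrawal from the study, for all three groups, counted from the primary withdrawal reason that Protocol 4.4 requires in the eCRF. Where the responsible AE can be identified from the recorded data, add a SOC/PT summary or a listing; otherwise report the count alone.

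Keep Tables 3.8, 3.12 and 3.16 and Listing 20 for TC and for TH after re-start. Print *not applicable*, not 0, for LTD and for the TH holiday phase. State how an AE is counted when it causes withdrawal during the holiday, prevents re-start, or begins in the holiday and leads to stopping after re-start. State which AE tables include LTD.

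The cost is SAP wording and table programming. The count itself uses data already recorded; the SOC/PT link may not be recoverable for every subject. The display would depart slightly from the programme standard.

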8.2. Adverse Events of Special Interest Analyses

8.2.1. Endpoint / Variables

8.2.1.1. Adverse Events of Special Interest

A comprehensive list of MedDRA terms based on clinical review will be used to identify each type of event. Changes to the MedDRA dictionary may occur between the start of the study and the time of reporting and/or emerging data from on-going studies may highlight additional adverse events of special interest, therefore the list of terms to be used for each event of interest and the specific events of interest will be based on the safety review team (SRT) agreements in place at the time of reporting. The details of the planned displays are provided in Appendix 11: List of Data Displays.

Adverse events of special interest for belimumab have been identified over the course of the development program. The Benlysta Program Safety Analysis Plan (PSAP) includes the definitions and adjudication criteria for the AESI. The definitions are based on standard and custom MedDRA queries (SMQs and CMQs). Categorizations for the AESI are listed in Section 13.9.

GSK will adjudicate neoplasms of unspecified malignancy, opportunistic infections, herpes zoster, serious suicide, and serious PISR events as described in the PSAP. In addition, GSK will review malignancy events to prevent counting an event multiple times in the case where a given malignancy has multiple events (e.g., a diagnostic test and the diagnosis). GSK will review all fatal events and assign a category of death.

